6.6.3.5 Management of Proteinuria

Regular assessment of proteinuria should be conducted as detailed in the SoA (Section 1.3). Guidelines for assessment and management of proteinuria are as follows:

Detection and Confirmation

- 1. Perform urine dipstick testing or urinalysis per the SoA (Section 1.3). Urine dipstick testing is the preferred method for testing for urinary protein, however, urinalysis may be used if the use of urine dipstick is not feasible.
- 2. A 24-hour urine collection initiated as soon as possible and at least within 72 hours (or an immediate spot UPCR test) is required in the following situations:
 - The first (initial) occurrence of ≥2+ (≥100 mg/dL) proteinuria on urine dipstick (or urinalysis) while the participant is receiving lenvatinib.
 - A subsequent increase in severity of urine dipstick or urinalysis proteinuria occurring on the same lenvatinib dose level.
 - When there has been a lenvatinib dose reduction and at the new dose level the urine protein dipstick result is ≥2+ (≥100 mg/dL). A 24-hour urine collection (initiated as soon as possible and at least within 24 hours) to verify the grade of proteinuria is required when UPCR is ≥2.4.

Grading of Proteinuria

Grading according to NCI CTCAE v5.0 will be based on the 24-hour urinary protein result if one has been obtained. If the participant has a 4+ proteinuria by dipstick (≥1000 mg/dL by urinalysis), a 24-hour urinary protein result is required to confirm Grade 3 proteinuria. Management of lenvatinib administration will be based on the grade of proteinuria according to Table 8.

Monitoring

- Urine dipstick testing or urinalysis for participants with proteinuria ≥2+ (≥100 mg/dL) should be performed Q2W (or more frequently as clinically indicated) until the results have been 1+ (30 mg/dL) or negative for 6 weeks.
- Proteinuria monitoring can be performed at the local laboratory or investigator site but must be managed by the site physician.
- In the event of nephrotic syndrome, lenvatinib must be discontinued.
- If proteinuria does not resolve, a nephrology consultation is recommended.

6.6.3.6 Management of Diarrhea

An antidiarrheal agent should be recommended to the participant at the start of study treatment and participants should be instructed and educated to initiate antidiarrheal treatment at the first onset of soft bowel movements. The choice of antidiarrheal agent should

be individualized to the participant's clinical circumstances and follow standard medical practice. If signs/symptoms of diarrhea persist despite optimal medical management, instructions contained in Table 8 should be followed.

6.6.3.7 Management of Hepatotoxicity

Liver function tests (ALT, AST, bilirubin levels) should be conducted as detailed in the SoA (Section 1.3) and as clinically indicated. If signs/symptoms indicating liver injury occur, instructions contained in Table 8 and Table 9 should be followed. Appropriate supportive care should be provided together with close monitoring. If hepatic failure (any grade per NCI CTCAE v5.0) occurs, lenvatinib must be discontinued. Hepatic failure is defined as per the CTCAE definition.

6.6.3.8 Management of Thromboembolic Events

Participants should be advised to pay attention to symptoms suggestive of venous thromboembolic events, which include acute onset of shortness of breath, dyspnea, chest pain, cough, hemoptysis, tachypnea, tachycardia, cyanosis, deep vein thrombosis signs including lower extremity swelling, and warmth to touch or tenderness. If any of these symptoms appear, participants should be instructed to report such symptoms promptly to the treating physician. If a thromboembolic event is confirmed, instructions contained in Table 8 should be followed. Appropriate supportive care should be provided together with close monitoring. If a participant experiences a Grade 3 or a life-threatening (Grade 4) thromboembolic reactions, including pulmonary embolism, lenvatinib must be discontinued.

Arterial thromboembolic events (eg, new onset, worsening, or unstable angina, myocardial infarction, transient ischemic attack, and cerebrovascular accident) of any grade require lenvatinib discontinuation.

6.6.3.9 Management of Posterior Reversible Encephalopathy Syndrome/Reversible Encephalopathy Syndrome/ Reversible Posterior Leukoencephalopathy Syndrome

PRES/RPLS is a neurological disorder that can present with headache, seizure, lethargy, confusion, altered mental function, blindness, and other visual or neurological disturbances. Mild to severe hypertension may be present. MRI is necessary to confirm the diagnosis of PRES/RPLS. Appropriate measures should be taken to control BP. In participants with signs or symptoms of PRES/RPLS, instructions in Table 8 should be followed.

6.6.3.10 Management of Hypocalcemia

Serum calcium should be monitored per the SoA (Section 1.3). Corrected serum calcium should be used to assess the grade of hypocalcemia per NCI CTCAE v5.0, using the following formula:

Corrected calcium = ($[4 - \text{serum albumin in g/dL}] \times 0.8 + \text{serum calcium}$)

The formula is not applicable when serum albumin concentration is normal (>4 g/dL); in such situations, the total (uncorrected) serum calcium should be used instead.

Hypocalcemia should be treated per institutional guidelines (eg, using appropriate calcium, magnesium, and vitamin D supplementation) until resolution.

6.6.3.11 Management of Hemorrhage

Guidelines in Table 8 should be followed for the management of hemorrhage. Either resume at a reduced dose or discontinue lenvatinib depending on the severity and persistence of hemorrhage.

6.6.3.12 Management of Gastrointestinal Perforation or Fistula Formation

Participants with gastric cancer are at increased risk for GI perforation and fistula formation. Lenvatinib should be discontinued in any participants who develop GI perforation of any grade or Grade 4 fistula.

6.6.3.13 Management of Palmar-plantar Erythrodysesthesia Syndrome

PPES is common across TKI therapies, and the strategies used for managing PPES in participants receiving TKIs (lenvatinib) range from preventative measures to topical medication once it has developed [Lacouture, M. E., et al 2014] [Lacouture, M. E., et al 2008].

Participants should be educated about the visible signs of PPES to help with the early detection of symptoms [Lacouture, M. E., et al 2014]. During treatment, participants should be encouraged to reduce exposure of the hands and feet to hot water, avoid tight footwear, and limit damage caused by vigorous exercise. Prophylaxis may include pretreatment examination of the soles of the feet and palms and removal of any existing hyperkeratotic areas and calluses present, which can then be protected by cushioning and treated with moisturizing creams and keratolytic agents [Lacouture, M. E., et al 2008]. A suggested treatment algorithm for PPES is outlined in Figure 5.

As most participants develop PPES within the first 2 to 4 weeks of initiating TKI therapy, avoiding traumatic activity and having sufficient rest during this time may be important [Lacouture, M. E., et al 2008]. PPES management can require dose reduction or interruption of lenvatinib treatment until the AE has resolved back to ≤Grade 1 severity [Lacouture, M. E., et al 2008]. It may also be appropriate to consult with a dermatologist and/or podiatrist for participants experiencing persistent Grade 2 or Grade 3 PPES.

Grade 1 Numbness Continue treatment at current dose **Tingling** and monitor for change in severity Dysesthesia Paresthesia Urea 10% to 20% cream twice daily Painless swelling and clobetasol 0.05% cream once daily Erythema Discomfort of hands or feet Reassess after 2 weeks (either by health care professional or patient No interference in ADL self-report); if reactions worsen or do not improve proceed to next step Continue treatment at current dose and monitor for change in severity Grade 2 Urea 20% cream twice daily Painful erythema Topical lidocaine 4% twice daily OR daily lidocaine patch 5% and Swelling of hands clobetasol 0.05% cream once daily to erythematous areas; pain control with NSAIDs/GABA agonists/narcotics and/or feet Interferes with patient's ADI Reassess after 2 weeks (either by health care professional or patient self-report); if reactions worsen or do not improve proceed to next step Grade 3 Interrupt treatment until severity decreases to grades 0 or 1: continue treatment of skin reaction with the following Moist desquamation Ulceration Blistering Topical lidocaine 4% twice daily OR daily lidocaine patch 5% and clobetasol 0.05% cream once daily; pain control Severe pain of hands with NSAIDs/GABA agonists/narcotics and/or feet Patient unable to Reassess after 2 weeks (either perform ADL by health care or patient self-report); if reactions worsen or do not improve,

Figure 5 Treatment Algorithm for Palmar-Plantar Erythrodysesthesia

ADL=activities of daily living; CTCAE=Common Terminology Criteria for Adverse Events; GABA=gamma-aminobutyric acid; NSAIDs=nonsteroidal anti-inflammatory drugs.

dose modification per product label may be necessary

Source: [Lacouture, M. E., et al 2014] [Lacouture, M. E., et al 2008]

6.6.3.14 Management of Osteonecrosis of the Jaw

Perform an oral examination prior to treatment with lenvatinib and periodically during lenvatinib treatment. Advise participants regarding good oral hygiene practices. Avoid invasive dental procedures, if possible, while on lenvatinib treatment, particularly in participants at higher risk. For participants requiring invasive dental procedures, discontinuation of bisphosphonate treatment may reduce the risk of ONJ. Withhold

MK-7902-015-08 FINAL PROTOCOL 10-JUN-2025 Confidential

08ZFCS

lenvatinib if ONJ develops and restart based on clinical judgment of adequate resolution (see Section 6.6.3.15).

6.6.3.15 Other Allowed Dose Interruptions for Lenvatinib

If the participant is receiving treatment with lenvatinib and requires surgery during the study, the stop time and restart time of lenvatinib should be as follows:

- For minor procedures: stop lenvatinib at least 2 days before the procedure and restart it at least 2 days after, once there is evidence of adequate healing and no risk of bleeding.
- For major procedures: stop lenvatinib at least 1 week (5 half-lives) prior to surgery and then restart it at least 2 weeks after, once there is evidence of adequate healing and no risk of bleeding.
- For participants who experience hand-foot syndrome that is related to both capecitabine and lenvatinib dosing, it is recommended that the capecitabine dose be reduced first, as described in Table 10.

6.6.4 Dose Modifications for Overlapping Toxicities

In this study, participants will be administered multiagent/multitargeted anticancer therapy. Although ample safety data are available for each of the components of recommended treatment regimens, the combination of all treatment medications is expected to have potential overlapping toxicities. As this study is open-label, participant safety will be actively monitored, as well as reviewed by an eDMC. A 21-day Safety Run-in including approximately 12 participants will evaluate safety as detailed in Section 4.1. Potential expected overlapping toxicities for participants on this study may include, but not limited to, hematologic, GI toxicity, cardiac toxicity, skin toxicity, and renal toxicity.

6.6.4.1 Lenvatinib and Pembrolizumab

Based on the known toxicity profiles of lenvatinib and pembrolizumab, certain treatment-related AEs are uniquely associated with one drug versus the other. For example, hypertension, arterial thrombotic events, proteinuria, and hemorrhagic events are known risks for lenvatinib treatment, while irAEs are risks for pembrolizumab treatment. However, certain AEs, such as diarrhea, hypothyroidism, and liver enzyme elevation, may be initially considered attributable to either study drug. Therefore, evaluation of attribution is important for determining the study drug most likely related to the AE, or an alternative etiology, and subsequently proper clinical management. The following aspects should be considered:

1. Timing of AE onset

- Because lenvatinib dosed daily and continuously due to a relatively short half-life (28 hours), and pembrolizumab is dosed Q6W due to a long half-life, lenvatinib can be interrupted to assess whether an AE improves/resolves with dechallenge (ie, interruption of treatment) based on the following 2 scenarios:
 - If an AE is identified during a treatment cycle (ie, between 2 pembrolizumab doses), only lenvatinib dose interruption is needed.

MK-7902-015-08 FINAL PROTOCOL 10-JUN-2025

Confidential

123

- If an AE is identified at the beginning of a treatment cycle, lenvatinib can be interrupted and dosing of pembrolizumab should be held.

If the participant recovers from an AE in response to lenvatinib interruption (ie, positive dechallenge), the event is more likely to be related to lenvatinib. Otherwise, after excluding other alternative explanations, an immune-related AE should be considered.

2. Severity of AE

If an AE is suspected to be treatment-related and is severe/life-threatening at the time of onset or is rapidly worsened, action including interrupting both drugs and initiating treatment with a corticosteroid (with exception of hypothyroidism, Type 1 diabetes mellitus) and other supportive care should be taken promptly.

- 3. Participants receiving combination therapy (lenvatinib + pembrolizumab) must discontinue study intervention if any of the following occur:
 - a. ALT or AST >5 X ULN for more than 2 weeks. Pembrolizumab will have already been permanently discontinued per Table 5, but lenvatinib may be administered at a reduced dose by the time this criterion is met and must be permanently discontinued immediately.
 - b. ALT or AST >3 × ULN and (TBL >2 × ULN or INR >1.5). Although Table 5 advises pembrolizumab to be withheld (interrupted), Table 8 and Table 9 advises lenvatinib to have no dose modification or a reduction, if this criterion is met, both drugs must be permanently discontinued immediately.

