Contraceptive use by women should be consistent with local regulations regarding the methods of contraception for those participating in clinical studies. If the contraception requirements in the local label for any of the study drugs is more stringent than the requirements above, the local label requirements should be followed.

Informed Consent

8. The participant (or legally acceptable representative) has provided documented informed consent/assent for the study.

Additional Categories

- 9. Has a performance status of 0 or 1 on the ECOG Performance Scale within 3 days prior to the first dose of study treatment.
- 10. Has provided a tumor tissue sample for PD-L1 and MSI biomarker analysis. If the initial tissue is inadequate for the analysis, an additional specimen will need to be provided.

- 11. Has adequately controlled BP with or without antihypertensive medications, defined as $BP \le 150/90$ mm Hg and no change in antihypertensive medications within 1 week prior to randomization.
- 12. Has adequate organ function as defined in the following table (Table 3). Specimens must be collected within 10 days prior to the start of study intervention.

Table 3 Adequate Organ Function Laboratory Values

System	Laboratory Value
Hematological	
Absolute neutrophil count (ANC)	≥1500 /mcL
Platelets	≥100,000 /mcL
Hemoglobin	≥9 g/dL or ≥5.6 mmol/L ^a
Renal	
Calculated ^b creatinine clearance	≥50 mL/min
Hepatic	
Total bilirubin	≤1.5 X ULN OR Direct bilirubin ≤ ULN for participants with total bilirubin levels >1.5 ULN
AST (SGOT) and ALT (SGPT)	≤2.5 X ULN OR ≤5 X ULN for participants with liver metastases
Albumin ^c	≥3.0 g/dL
Coagulation	
International Normalized Ratio (INR) or Prothrombin Time (PT) Activated Partial Thromboplastin Time (aPTT)	≤1.5 X ULN unless participant is receiving anticoagulant therapy as long as PT or PTT is within therapeutic range of intended use of anticoagulants ≤1.5 X ULN unless participant is receiving anticoagulant therapy as long as PT or PTT is within therapeutic range of intended use of anticoagulants

ALT (SGPT)=alanine aminotransferase (serum glutamic pyruvic transaminase); AST (SGOT)=aspartate aminotransferase (serum glutamic oxaloacetic transaminase); GFR=glomerular filtration rate; ULN=upper limit of normal.

$$\frac{\text{(140-age [years]} \times \text{weight [kg])}}{\text{Serum creatinine (mg/dL)} \times 72} (\times \text{ F})^*$$

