8.4.6 Disease-related Events and/or Disease-related Outcomes Not Qualifying as AEs or SAEs

Efficacy endpoints as outlined in Section 3 will not be reported to the Sponsor as AEs/SAEs.

154

Specifically, the suspected/actual events covered in this exception include any event that is progression of the cancer under study.

The Sponsor will ensure that aggregated efficacy endpoint events and safety data are monitored to safeguard the participants in the study.

8.4.7 **Events of Clinical Interest**

Selected serious and nonserious AEs are also known as ECIs and must be reported to the Sponsor.

ECIs for this study include:

- An overdose of Sponsor's product, as defined in Section 8.5; lenvatinib overdose without an associated AE is not considered an ECI.
- All potential DILI events meeting biochemical criteria of Hy's Law will be reported to the Sponsor, regardless of suspected etiology, as both an ECI and SAE, with OME criteria in the absence of other SAE criteria, within 24 hours of learning of the event. Potential DILI events are defined as:
- An elevated AST or ALT laboratory value that is greater than or equal to 3× the ULN
- An elevated total bilirubin laboratory value that is greater than or equal to 2× the ULN and,
- At the same time, an alkaline phosphatase laboratory value that is less than 2× the ULN, determined by way of protocol-specified laboratory testing or unscheduled laboratory testing.*

*Note: These criteria are based on available regulatory guidance documents. The purpose of the criteria is to specify a threshold of abnormal hepatic tests that may require an additional evaluation for an underlying etiology. The study-site guidance for assessment and follow up of these criteria can be found in the Investigator Study File Binder (or equivalent).

8.5 **Treatment of Overdose**

For purposes of this study, an overdose will be defined as any dose exceeding the prescribed dose for

- Pembrolizumab: any dose of 1000 mg or greater
- Lenvatinib: any dose above the protocol-prescribed dose if associated with an AE

There is no specific antidote for an overdose of lenvatinib. Due to its high degree of plasma protein binding, lenvatinib is not expected to be dialyzable. Adverse reactions in participants receiving single doses of lenvatinib as high as 40 mg were similar to those in clinical studies

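### Table 3 admits some participants with liver metastases whose entry values already literally meet the permanent-stop rule in Section 6.6.4.1 item 3b, and the protocol does not say how those values are to be handled

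*Combined protocol and SAP*

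**What the plan says.** **Entry (Section 5.1, Table 3).** AST and ALT may be up to 2.5×ULN, or "≤5 X ULN for participants with liver metastases". Total bilirubin may be up to 1.5×ULN; the alternative is "Direct bilirubin ≤ ULN for participants with total bilirubin levels >1.5 ULN", which sets no upper limit on total bilirubin. INR or PT must be "≤1.5 X ULN unless participant is receiving anticoagulant therapy as long as PT or PTT is within therapeutic range of intended use of anticoagulants".

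**Stop rule (Section 6.6.4.1, item 3b).** Participants on lenvatinib plus pembrolizumab "must discontinue study intervention if any of the following occur", and item 3b is "ALT or AST >3 × ULN and (TBL >2 × ULN or INR >1.5"). It acknowledges that Table 5 only withholds pembrolizumab and that Tables 8 and 9 leave lenvatinib unchanged or reduced, and then says that "if this criterion is met, both drugs must be permanently discontinued immediately".

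**Related text.** The Table 5 footnotes grade AST, ALT and bilirubin as multiples of baseline when baseline is abnormal. Section 8.4.7 defines a potential Hy's Law event by AST or ALT at least 3×ULN, alkaline phosphatase below 2×ULN and "An elevated total bilirubin laboratory value that is greater than or equal to 2× the ULN". The Schedule of Activities has PT/INR at screening and afterwards only as needed for participants on warfarin.

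**The concern.** An entry criterion and a mandatory stop for the same laboratory values should not overlap unless the protocol says what happens in the overlap. Here they do. Item 3b is a threshold rule with no baseline term, no exception for anticoagulation and no exception for isolated unconjugated bilirubin, although Table 3 makes allowance for all three situations. INR is a multiple of ULN in Table 3 and a bare number in item 3b.

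At stake is consistent use of a liver-safety rule. One site could permanently stop both drugs in a participant whose values have not moved since screening. Another could set the rule aside in the same situation, relying on Table 5. Section 7.1 makes discontinuation irreversible, so the difference matters to each person affected. The reason recorded for such a discontinuation would also be hard to interpret.

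**Working it through.** No planned figure has to be reproduced. The check is whether any set of values passes Table 3 and also meets item 3b.

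**Conditions** (liver values in multiples of ULN)
- Eligible: (AST/ALT ≤2.5, or ≤5 with liver metastases) and (total bilirubin ≤1.5, or direct bilirubin ≤1) and (INR ≤1.5 × INR ULN, or anticoagulated in therapeutic range).
- Item 3b: AST or ALT >3 and (total bilirubin >2 or INR >1.5).

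**Illustrative profiles**

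| Profile | Meets Table 3 | Meets 3b |
|---|---|---|
| A. Liver metastases, ALT 4, bilirubin 1, INR 2.5 on anticoagulant in range | yes | yes |
| B. Liver metastases, ALT 4, bilirubin 2.5, direct bilirubin 0.8, INR 1.0 | yes | yes |
| C. Liver metastases, ALT 4, INR 1.6, INR ULN 1.1, no anticoagulant | yes | yes |
| D. No liver metastases, ALT 2.5, INR 2.5 on anticoagulant in range | yes | no |
| E. Liver metastases, ALT 3.0, INR 2.5 on anticoagulant in range | yes | no |

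The overlap is confined to liver metastases with AST or ALT above 3 and up to 5×ULN. Item 3a (above 5×ULN for more than two weeks) does not overlap, because entry is capped at 5×ULN.

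**INR units (profile C).** The documents give no INR ULN, so it is assumed. Table 3 cap = 1.5 × ULN; gap = cap − 1.5.

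| Assumed INR ULN | Table 3 cap | Gap above 1.5 |
|---|---|---|
| 1.0 | 1.50 | 0 |
| 1.1 | 1.65 | 0.15 |
| 1.2 | 1.80 | 0.30 |
| 1.3 | 1.95 | 0.45 |

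This route needs an INR ULN above 1.0. It also has no scheduled post-baseline INR to act on, because later testing is tied to warfarin. It is mostly theoretical.

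**What Table 5 does with the same values.** An unchanged ALT of 4×ULN is 4/4 = 1.0× baseline. With an abnormal baseline, Grade 2 starts above 3.0× baseline, that is above 3 × 4 = 12×ULN. An unchanged bilirubin of 2.5×ULN is 1.0× baseline, and Grade 2 starts above 1.5 × 2.5 = 3.75×ULN. Table 5 therefore calls for no action where item 3b, read literally, calls for a permanent stop.

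**Size.** The documents give no prevalence. Assume 30–40% have liver metastases, 5–10% of those have AST/ALT in the 3–5×ULN band, and 5–10% of those have INR >1.5 or isolated unconjugated bilirubin >2×ULN. With 880/2 = 440 in Arm 1:
- Low: 0.30 × 0.05 × 0.05 = 0.00075; × 440 = 0.3 participants.
- High: 0.40 × 0.10 × 0.10 = 0.004; × 440 = 1.8 participants.

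**The case against.** The best defence is that item 3b is about new on-treatment events. It sits in a section on overlapping toxicities and attribution, it is triggered when something happens, and it describes a case in which Table 5 already withholds pembrolizumab. Unchanged abnormal entry values do not fit that description. This reading is plausible and may be what the sponsor meant, but item 3b does not state it. Its operative condition is that the criterion is met, and a mandatory permanent stop should not depend on inference. Exclusion criterion 24 could keep such people out, but it is left to investigator judgment. Tables 8 and 9 are not available to us, but item 3b says that it applies despite them.

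Other parts of the defence succeed, and they rule out stronger readings that a reader might infer:

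- *A Hy's Law SAE at entry.* Under Table 13, a potential DILI event before randomization is reportable only if it is due to intervention or causes exclusion. Values that Table 3 accepts do neither. What stays open is total bilirubin at or above 2×ULN persisting on treatment, because Section 8.4.7 disregards etiology.
- *Inflated Arm 1 SAE counts.* The Section 8.4.7 definition applies to both arms and also requires alkaline phosphatase below 2×ULN.
- *Diluted exposure or biased efficacy.* About 0 to 2 people in 440 cannot do this materially. The primary PFS analysis does not count discontinuation as an event, and OS is analysed by intention to treat. Only PFS sensitivity analysis 2 counts such a discontinuation, and only without documented progression or death. The rule falls on one arm because only that arm receives these drugs.
- *Rewriting Table 3 would protect future participants.* Section 9.9 states that enrollment is complete.

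**Conclusion.** The conflict between Table 3 and item 3b is real, by two practical routes: a therapeutic INR above 1.5 on an anticoagulant, and total bilirubin above 2×ULN with normal direct bilirubin, each with liver metastases and AST/ALT above 3 and up to 5×ULN. The third route, through the INR units, is mostly theoretical. The logical overlap rests on the documents alone. The count of about 0.3 to 1.8 Arm 1 participants rests on assumed rates and could be wrong in either direction. The effect on efficacy results and overall SAE counts is negligible. The point is worth acting on because the stop is mandatory and irreversible for each person, the text supports opposite actions, and the remedy is cheap. No view is taken on which threshold is right.

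**What to change.** 1. The sponsor should reconcile Table 3 with Section 6.6.4.1 item 3b, and express INR in one unit in both.
2. State explicitly how values present at entry, and a therapeutic INR on an anticoagulant, are handled under item 3b. With enrollment complete, the useful vehicle is a clarification to sites with participants still on treatment.
3. Check Section 8.4.7 for total bilirubin at or above 2×ULN that persists from baseline into treatment, and state how it is reported.
4. In the CSR, list Arm 1 participants whose baseline values met item 3b. Flag any resulting discontinuation in the summary of discontinuations due to AEs and in PFS sensitivity analysis 2.

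The cost is wording in two or three places, one site letter and one listing. Steps 1 to 3 need no new data, and step 4 uses baseline laboratory and discontinuation data that the study already collects.
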